### 5.1.8 Patient Global Impression of Change in Dyspnea

The patient global impression of change (PGI-C) in dyspnea is a 1-item questionnaire designed to assess the patient's impression of change in dyspnea.

The patient global impression of change asks the patient to choose one response that best describes the change (if any) in his/her shortness of breath when performing usual activities since he/she started taking the trial medication on the following 7-category scale:

- Very much better (+3)
- Much better (+2)
- A little better (+1)
- No change (0)
- A little worse (-1)
- Much worse (-2)
- Very much worse (-3)

Please refer to [section 6.2.2](#) for order of completion of patient reported outcome measures and [Appendix 10.3.4](#).

### 5.1.9 Patient Global Impression of Severity of Heart Failure Symptoms

Patient global Impression of Severity (PGI-S) of Heart Failure Symptoms is a 1-item questionnaire to assess patient's impression of symptoms severity, specifically: shortness of breath, fatigue and swelling.

The PGI-S asks the patient to choose one response that best describes how his/her Heart Failure Symptoms, specifically: shortness of breath, fatigue and swelling are now on a 5-point scale:

- Not at all (1)
- Mild (2)
- Moderate (3)
- Severe (4)
- Very severe (5)

Please refer to [section 6.2.2](#) for order of completion of patient reported outcome measure and [Appendix 10.3.5](#).

### 5.1.10 Patient Global Impression of Severity of Dyspnea

Patient global Impression of Severity (PGI-S) of Dyspnea is a 1-item questionnaire designed to assess patient's impression of symptom severity, specifically dyspnea.

The PGI-S item asks the patient to choose one response that best describes how his/her dyspnea is now on a 5-point scale:

- Not at all (1)
- Mild (2)
- Moderate (3)

- Severe (4)
- Very severe (5)

Please refer to [section 6.2.2](#) for order of completion of patient reported outcome measures and [Appendix 10.3.6](#).

#### 5.1.11 Clinician Global Impression of Change in CHF Severity

Clinician Global Impression of Change in CHF Severity is a 1-item questionnaire designed to assess Investigator's (physician's) overall impression of change in the patient's chronic heart failure (CHF) severity related to his/her participation in the study; specifically signs and symptoms associated with chronic heart failure on a 7-point scale.

This questionnaire is assessing change from baseline. For consistency, the same Investigator should assess the patient at each visit. If this is not possible, then the response 'N/A = cannot be assessed' should be selected.

- N/A = Cannot be assessed
- 1 = Very much improved
- 2 = Much improved
- 3 = Minimally improved
- 4 = No change
- 5 = Minimally worse
- 6 = Much worse
- 7 = Very much worse

Please refer to [section 6.2.2](#) for preferred order of completion of assessments and [Appendix 10.4.1](#).

#### 5.1.12 Clinician Global Impression of Severity of CHF

Clinician Global Impression of Severity of CHF is a 1-item questionnaire designed to assess Investigator's overall impression of severity of chronic heart failure, specifically signs and symptoms associated with chronic heart failure now (at the time-point of assessment) on the 5-point scale:

- Normal, not at all ill (1)
- Mildly ill (2)
- Moderately ill (3)
- Severely ill (4)
- Very severely ill (5)

Please refer to [section 6.2.2](#) for preferred order of completion of assessments and [Appendix 10.4.2](#).

## 5.2 ASSESSMENT OF SAFETY

### 5.2.1 Physical examination

A complete physical examination will be performed at the time points specified in the [flowchart](#). Complete physical examination will include general appearance as well as evaluation of organ systems including an assessment of the cardiovascular system

The results must be included in the source documents available at the site.

### 5.2.2 Vital signs

Vital signs will be evaluated at the time points specified in the [flowchart](#). This includes systolic and diastolic blood pressure and pulse rate (electronically or by palpation count for 1 minute) in a seated position after 5 minutes of rest.

All recordings should be made using a similar type of and validated certified blood pressure recording instrument on the same arm. Further details on blood pressure measurement procedure are provided [Appendix 10.6](#).

### 5.2.3 Body weight and height

Measurements of body weight and height will be performed at the time points specified in the [flowchart](#).

BMI ( $\text{kg}/\text{m}^2$ ) will be calculated for determination of eligibility at Visit 1.

Body weight should be measured as follows:

- after the urine sampling (weight after bladder voiding),
- shoes and coat/jackets should be taken off, and
- pockets should be emptied of heavy objects (i.e. keys, coins etc.).

### 5.2.4 Safety laboratory parameters

Safety laboratory parameters to be assessed are listed in [Table 5.2.4:1](#). For the sampling time points please see the [flowchart](#).

All analyses will be performed by a central laboratory, the respective reference ranges will be provided in the ISF.

Patients do not have to be fasted for the blood sampling for the safety laboratory. Instructions regarding sample collection, sample handling/ processing and sample shipping are provided in the Laboratory Manual in the ISF.

The central laboratory will send reports to the investigator. It is the responsibility of the investigator to evaluate the laboratory reports. Clinically relevant abnormal findings as judged by the investigator will be reported as adverse events (please refer to [Section 5.2.7.1](#)).

In case the criteria for hepatic injury are fulfilled, a number of additional measures will be performed (please see [Section 5.2.7.1](#) and the DILI Checklist provided in the ISF and eDC system. The amount of blood taken from the patient concerned will be increased due to this additional sampling.

The central laboratory will transfer the results of the analysis to the sponsor.

Table 5.2.4:1 Safety laboratory tests

Haematology

• Hematocrit

• Haemoglobin

- Reticulocyte Count (reflex test if Hb outside normal range)

• Red Blood Cells (RBC) / Erythrocytes

• WBC / Leukocytes

• Platelet Count / Thrombocytes

• Differential Automatic (relative and absolute count): Neutrophils, Eosinophils, Basophils, Monocytes, Lymphocytes

Clinical chemistry

• Albumin

• Alkaline phosphatase

- <math>\gamma</math>-GT (gamma-glutamyl transferase) reflex test triggered by elevated alkaline phosphatase on two sequential measures

• ALT (alanine transaminase, SGPT)

• AST (aspartate transaminase, SGOT)

• Bicarbonate

• Bilirubin total, fractionated if increased

• Chloride

• Creatinine

• Creatine kinase (CK)

• Hs Troponin I (reflex tests if CK is elevated)

• Glucose

• Potassium

• Protein total

• Sodium

• Urea (BUN)

• Uric acid

Urine


• Urinalysis: standard dipstick test including ketones semi-quantitative measurement

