## FLOW CHART

Trial Period	Screening*	Randomized Treatment Period				FU Period
		1	2	3	4 (EOT)	
Visit	1	2	3	4 (EOT)	Early Discontinuation on Visit 	FU Visit
Trial week	-3	1	6	12		EOT/early d/c + 7 days
Days of treatment	-21 to -4	1	43	85		
Time Window	-	-	±7	±7		+7
Informed consent	X					
In/exclusion criteria	X	X				
Demographics	X					
Medical history/Concomitant diagnoses	X					
Vital signs 	X	X	X	X	X	X
Physical examination	X	X		X	X	
Height	X					
Weight	X	X		X	X	
Urine Pregnancy test 	X	X	X	X	X	
HbA1c		X		X	X	
eGFR (CKD-EPIcr formula)	X 	X	X	X	X	X
Safety lab: blood tests	X 3*	X	X 	X	X	X
Safety lab: urinalysis including ketones	X 	X	X	X	X	X
ECG exam 	X 			X	X	
Echocardiogram 	X					
NT-proBNP	X 	X	X	X	X	
6 min walk test 	X 	X 	X	X 	X	
Concomitant therapy	X	X	X	X	X	X
Adverse events	X	X	X	X	X	X
KCCQ 		X	X	X	X	
CHQ-SAS 		X	X	X	X	
Clinical Congestion Score		X	X	X	X	
Patient Global Impression of Severity of Heart Failure Symptoms 		X	X	X	X	
Patient Global Impression of Severity of Dyspnea 		X	X	X	X	
Patient Global Impression of Change in Heart Failure Symptoms 			X	X	X	

Trial Period	Screening*	Randomized Treatment Period				FU Period
Visit	1	2	3	4 (EOT)	Early Discontinuation on Visit 	FU Visit
Trial week	-3	1	6	12		EOT/early d/c + 7 days
Days of treatment	-21 to -4	1	43	85		
Time Window	-	-	±7	±7		+7
Patient Global Impression of Change in Dyspnea 			X	X	X	
Clinician Global Impression of Severity of CHF		X	X	X	X	
Clinician Global Impression of Change in CHF Severity			X	X	X	
NYHA Classification	X	X	X	X	X	
HCRU		X	X	X	X	
Randomization (IRT)		X				
Dispense trial medication		X	X			
Return medication / Medication compliance check			X	X	X	

\* The screening procedures can be performed on different days within the time window. Specifically it is recommended to have the NT-proBNP and safety lab measures (via central lab) measured as first step, especially in patients with no previous natriuretic peptide value available from clinical routine assessment in the past 6 months (refer to [section 6.2.1](#)). The baseline rhythm (e.g. sinus rhythm, AF) of the patient must be clarified (i.e. ECG) and documented at the time the NT-proBNP sample is collected.

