1. Blood pressure and heart rate will be measured with the patient seated and rested for at least 5 minutes.
2. For female patients of child-bearing potential, local urine pregnancy test should be performed.
3. For the screening Visit 1, the safety laboratory is limited to liver transaminases, alkaline phosphatase, haemoglobin, serum creatinine, eGFR calculation. Patients do not have to be fasting.
4. For Visit 3, the safety laboratory is limited to liver transaminases, bilirubin and serum creatinine, eGFR calculation
5. A 12-lead ECG will be performed at screening and EOT visits. For this 12-lead ECG, the interpretation of the tracing must be made locally by the investigator or designee. In case of any cardiac symptom (indicating rhythm disorders or cardiac ischaemia), additional 12-lead ECG(s) should be done and any abnormal findings will be reported as AEs.
6. An echocardiogram should be performed on all patients at Visit 1 to assess left ventricular ejection fraction (LVEF) for eligibility.
7. 6MWT to be performed by qualified and experienced personnel. The assessments should be performed by the same qualified and experienced personnel at all visits, where possible.

- Testing of the 6MWT at each clinic visit should be preferably performed about the same time of day to minimize intraday variability. Prior to performing the 6MWT, the relative contraindications to exercise should be assessed as per [appendix 10.1.3](#). Heart rate and blood pressure will be measured before exercise, at end-exercise, five minutes after termination of exercise and when, for clinical reasons, it is required.
8. One 6 minute walk test (6MWT) will be performed at the screening visit. The 6MWT will be performed after vital signs have been captured and prior to any other study procedures at this visit. If the distance walked is > 350m the patient will be considered a screen failure.
  9. Two 6 minute walk tests will be performed at visits 2 and 4 at least 1 hour apart. The largest distance measured will be used for the analysis. If at Visit 2 the distance walked on any test is > 350m or the largest distance walked is < 100m the patient will be considered a screen failure.
  10. For the order of completion of patient reported outcome measures please refer to [section 6.2.2](#).

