#### 4.1.2 Selection of doses in the trial

Empagliflozin 10 mg and 25 mg are approved for the treatment of T2DM.

Empagliflozin exerts its effect by promoting glucosuria and consequent hemodynamic changes associated with diuresis, improvement in arterial stiffness, blood pressure lowering effect with no increase in HR and reduction in HR multiplied by pressure product, an index of myocardial oxygen consumption. These modes of actions support the scientific rationale of testing empagliflozin in patients with HF.

In the EMPA-REG-OUTCOME trial both doses were administered to patients with T2DM and showed to be equally effective in reducing CV death, HHF, and composite of HHF or CV death in patients with HF at baseline.

In subgroup analysis empagliflozin improved the main outcome of CV death and HHF with the similar magnitude in patients with low or high levels of HbA1c at baseline. This indicates the risk reduction for HF outcome is independent of the degree of glycaemic control at baseline, suggesting that these benefits can be achieved with the 10 mg dose similar to the 25 mg dose in the non-diabetic population as well. The mechanism of action is supported by studies in healthy volunteers where both doses were associated with a glucosuria of about 50g per day.

Given the lower exposure with 10 mg empagliflozin and similar general safety, and observed CV effects for both doses, empagliflozin 10 mg once daily has been selected as the dose in this trial.

For further details see current version of the IB [[c01678844-09](#)].

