#### **4.1.5 Blinding and procedures for unblinding**

##### **4.1.5.1 Blinding**

Patients, investigators and everyone involved in trial conduct or analysis or with any other interest in this double-blind trial will remain blinded with regard to the randomised treatment assignments until after database lock.

The DMC will be provided with unblinded data in order to allow them to review efficacy and safety and to fulfil their tasks as outlined in the data monitoring committee charter. An independent team, not otherwise involved in the conduct of the trial, will provide the unblinded results to the DMC.

The randomization code will be kept secret by Clinical Trial Support up to database lock.

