## 10. HISTORY TABLE

This is a revised TSAP including the following modifications to the final TSAP

Table 10: 1 History table

Version	Date (DD- MMM-YY)	Author	Sections changed	Brief description of change
FINAL	5-APR-19		None	This is the final TSAP
REVISED	21-OCT-19		Section 6.3 / Section 7.4 / Section 7.5	
Definition of Sensitivity analysis set 2 and Sensitivity analysis set 3
 
Reason for change:                      For a subset of patients, on-treatment urine dipstick test results for urine glucose had been transferred from the central laboratory to the sites before DBL. A positive urine glucose test can be suggestive of treatment allocation. Therefore, an additional sensitivity analysis is performed based on the subset of patients who did not have an on-treatment urine glucose measurement transferred to and accessed by the sites before DBL.                      In patients with diabetes mellitus at baseline, a positive urine dipstick test result is of limited value with respect to bearing potential information on treatment allocation. Therefore, a second additional sensitivity analysis is performed, which excludes those non-diabetic patients for whom at least one on-treatment urine glucose measurement was transferred to and accessed by the sites before DBL.

				
Reason for change:                      Clarification.
 
Reason for change:

Table 10: 1 History table (cont.)

Version	Date (DD- MMM-YY)	Author	Sections changed	Brief description of change
			Section 6.6	
Clarification of 6MWT if a patient performs the visit at week 12 but does not perform the 6MWT.
 
Clarification of handling of missing baseline questionnaires for WCI analyses.
 
Clarification of handling of SAE with outcome “recovered with sequelae” leading to an amputation.
 
Reason for change: Clarifications consistent with protocol.

			Section 6.7	
Clarification of time windows for laboratory values at day of treatment start, repeated values, and time windows for sensitivity analyses using primary analysis model.
 
Reason for Change: For laboratory values, clock time is recorded and therefore can be taken into account.
 
All models using Wilcoxon will use the same time window

			Section 7.8	
AEs will be coded using version 22.0 of the MedDRA coding dictionary.
 
Reason for Change: Clarification

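### The protocol sends the week 6 dipstick result to the investigator and states no rule masking urine glucose, so a site can infer likely allocation before week 12, mainly in non-diabetic patients

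*Protocol*

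**What the plan says.** Protocol 5.2.4 has the safety samples analysed centrally ("All analyses will be performed by a central laboratory") and routes the results to the site: "The central laboratory will send reports to the investigator. It is the responsibility of the investigator to evaluate the laboratory reports". Table 5.2.4:1 gives the urine panel as "Urinalysis: standard dipstick test including ketones semi-quantitative measurement". Ketones are named there; glucose is not.

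The flow chart row "Safety lab: urinalysis including ketones" is marked at every visit, including visit 3 (week 6). Footnote 4 says "For Visit 3, the safety laboratory is limited to liver transaminases, bilirubin and serum creatinine, eGFR calculation". That footnote is attached to the blood-test row and names blood analytes only, so the visit 3 urinalysis stands.

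Protocol 1.2 states that the urinary glucose effect lasts as long as the drug is used. Protocol 4.1.2 adds that in healthy volunteers "both doses were associated with a glucosuria of about 50g per day".

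Protocol 4.1.5.1 commits that patients, investigators and others involved "will remain blinded with regard to the randomised treatment assignments until after database lock". It gives no measure for urine glucose.

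SAP section 10 (revision of 21 October 2019) reports that on-treatment urine glucose results went from the central laboratory to sites before database lock for a subset of patients. It comments: "A positive urine glucose test can be suggestive of treatment allocation". It calls a positive result of limited value in patients with diabetes. SAP 6.3 then defines SensRS2 and SensRS3. SAP 7.4.2 and 7.5.1.2 apply them to the primary and key secondary endpoints.

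**The concern.** The dipstick glucose result is a direct readout of the drug's mechanism. A non-diabetic patient who is negative at visit 2 and positive at visit 3 is probably on empagliflozin. Followed as written, section 5.2.4 puts that information with the investigator about six weeks before the primary assessment.

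The walk test is self-paced, and Protocol 3.2 names this as a limitation. Staff may decide that a patient should not continue (Appendix 10.1.4), and the investigator judges contraindications (Appendix 10.1.3). A patient who attends week 12 but cannot perform the test for safety reasons is scored 0 m (Protocol 7.5). The clinical congestion score, the clinician global impressions and NYHA class are rated by the investigator, who also receives the report. Protocol 5.1.11 asks for the same investigator at each visit. At stake is the double blind for an effort-dependent primary endpoint and, more directly, for the clinician-rated endpoints.

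**Working it through.** **1. Timing.** Protocol 6.2.2 lists the laboratory sample last in the preferred visit order, after the questionnaires, clinician scales and walk test. For a patient who stays on treatment, week 6 is therefore the one scheduled on-treatment sample whose report can arrive before the week 12 assessments. The visit 4 report comes too late to affect them.

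**2. Masking rule.** Protocol 4.1.5.1, 5.2.4, Table 5.2.4:1, the flow chart and the SAP were set side by side. None withholds urine glucose from site reports. The protocol does not name glucose as a dipstick analyte, but the SAP shows that it was measured and transmitted.

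**3. How informative a result would be (assumed; the documents give no dipstick accuracy).** Under 1:1 allocation, the chance of guessing the arm correctly is (s + 1 − f)/2, where s is the positive rate on drug and f the positive rate on placebo. Take s = 0.90 to 0.99.
- Non-diabetic, f = 0.02 to 0.05: from (0.90 + 0.95)/2 = 0.925 to (0.99 + 0.98)/2 = 0.985.
- Diabetic, f = 0.30 to 0.60: from (0.90 + 0.40)/2 = 0.65 to (0.99 + 0.70)/2 = 0.845.

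This agrees with the SAP's distinction by diabetes status.

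**4. Reproducing the plan's design figures.** Inputs from Protocol 7.7: difference 30 m, SD 72 m, two-sided alpha 0.05, power 90%. P(X<Y) = Φ(−30/(72√2)) = 0.384. The rank-test formula gives n per group = (1.960 + 1.282)²/(6 × 0.116²) = 10.51/0.0807, rounded up to 131, as stated. For 40 and 50 m it gives 75 and 50, against 76 and 50 stated. Simulated power at 150 per group, with exactly 5, 8 or 10% per arm set to worst case, is 90.0, 87.2 and 84.8%, against 90, 87 and 85% stated. The same model is used below.

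**5. Illustration for the primary test.** True effect zero, 150 per arm, SD 72 m. Each patient is missing at random with probability 5% and ranked at the bottom. A spurious between-arm shift is applied to an exposed share of patients. There were 40,000 runs of the tie-corrected rank-sum test. The exposed shares and shifts are assumptions. With no shift, two-sided rejection is 5.1%.

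| Exposed share | 5 m | 10 m | 15 m |
|---|---|---|---|
| 25% | 5.4% | 5.9% | 6.7% |
| 50% | 6.0% | 8.1% | 12.7% |

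For scale, the average bias is share × shift: 0.25 × 5 = 1.25 m at the low end and 0.50 × 15 = 7.5 m at the high end. The standard error is 72 × √(2/150) = 8.31 m.

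**6. What the sensitivity sets can do.** With a true 30 m difference and 5% imputed, power in SensRS2 would be about 87, 79 or 61% if 10, 25 or 50% of patients were excluded. The sets select on a post-randomisation event (a result posted and accessed). They do not separate week 6 reports from reports seen after the week 12 test. SAP 7.5.2 and 7.6 do not apply them to the congestion score, clinician impressions or NYHA class.

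**The case against.** **Masking may exist elsewhere.** The protocol refers report and sample details to the Laboratory Manual and the ISF, which are not available. That only a subset of results was transferred would fit an intended suppression that failed. This stands: what can be said is that neither supplied document states a rule, not that none existed.

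**The primary and key secondary endpoints have protection.** Encouragement is scripted minute by minute, other words or body language are barred, and staff do not walk with the patient (Appendix 10.1.4). The person running the test need not be the one reading the report. KCCQ and CHQ-SAS are completed by the patient at the start of the visit, and the report goes to the site. This reduces the risk without removing it. The clinician-rated endpoints are more exposed but lie outside the confirmatory hierarchy.

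**The dipstick does not identify the arm.** A reader might infer that a positive result means empagliflozin and a negative one placebo. The SAP says only suggestive. The healthy-volunteer figure need not carry over to patients admitted with eGFR down to 20, and a patient who has stopped or missed treatment may also be negative.

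**The number exposed is unknown.** A reader might take the 25–45% T2DM figure in Protocol 1.1, count the other 55–75% (165–225 of 300) as unblinded, and pair the top share with a 15 m shift. The bias is then 0.75 × 15 = 11.25 m, and P(Z > 1.96 − 11.25/8.31) is about 27% for a false positive favouring empagliflozin. The documents do not support this. The T2DM figure is background epidemiology, the SAP reports only a subset, and the calculation stacks the highest assumed share on the highest assumed shift.

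**The direction is not fixed.** Background therapy may be adjusted, but according to guidelines (Protocol 6.2.2). Intensifying it in suspected placebo patients would shrink the difference.

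**Conclusion.** The point holds in limited form. As written, Protocol 5.2.4 lets a site see a week 6 result from which likely allocation can be inferred, mainly in non-diabetic patients. The blinding section has no stated measure against it, and the SAP confirms that some results reached sites before lock. The effect on the primary test cannot be quantified from the documents. Under the assumed shares and shifts, it runs from negligible (5.4%) to material (12.7%). SensRS2 and SensRS3 give a partial robustness check for the primary and key secondary endpoints; they do not restore the blind and leave the clinician-rated endpoints without one. The documents do not support a claim that the blind was lost for most patients or that bias in favour of empagliflozin is established. This is a cheap improvement to the plan.

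**What to change.** State in Protocol 5.2.4 and Table 5.2.4:1, with a cross-reference in 4.1.5.1, that urine glucose from every post-randomisation sample is suppressed until database lock on reports and portal views open to sites, monitors and the blinded trial team. Ketones and the other dipstick results stay reported. The laboratory keeps the glucose values in a masked data transfer available to the DMC.

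The cost is a short protocol rule and a central-laboratory report setting; the sample size does not change. There is a small downside. Sites lose on-study urine glucose, and no blood glucose is scheduled at visit 3 to take its place, because footnote 4 limits that visit's bloods. Blood glucose is in the full safety panel at visits 2 and 4.
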